9.3. Confidentiality

For security and confidentiality purposes, participants will be assigned an identifier that will be used instead of their name. Protected health information gathered for this study will be shared with the coordinating center, the Jaeb Center for Health Research in Tampa, FL. De-identified participant information may be provided to research sites involved in the study.

1084 CHAPTER 10: STATISTICAL CONSIDERATIONS

1085

1086 10.1. Statistical and Analytical Plans

1087 The approach to sample size and statistical analyses are summarized below. A detailed statistical
1088 analysis plan will be written and finalized prior to the completion of the study. The analysis plan
1089 synopsis in this chapter contains the framework of the anticipated final analysis plan.

1090 10.2. Statistical Hypotheses

- 1092 Null hypothesis: There will be no difference in percentage of CGM-measured glucose values
1093 <70 mg/dL between PLGS and SAP
- 1094 Alternate hypothesis: PLGS will improve the percentage of CGM-measured glucose values <70
1095 mg/dL over SAP.

1096 10.3. Sample Size

1097 Data from the JDRF Continuous Glucose Monitoring Randomized Clinical Trial was used to estimate
1098 SD and the frequency of time <70 mg/dL for the pump or MDI population. Assuming a crossover
1099 design with two 3 weeks periods, a 2-tailed test, a 33% relative reduction in 24-hour time <70 mg/dL,
1100 standard deviation of the paired differences = 3%, a type I error = 5%, and 90% power; a sample of 52
1101 participants is required.

1102 With a sample size of 90 participants, the primary analysis will have 99% power. The larger sample
1103 size will provide increased precision for safety analyses and subgroup analyses.

1104 10.4. Outcome Measures

1105 Primary Efficacy Endpoint:

- 1106 Percentage of sensor glucose values <70 mg/dL

1107 Secondary Efficacy Endpoints:

1108 *Hypoglycemia*

- 1109 Percentage of values <60 mg/dL
- 1110 Percentage of values <50 mg/dL
- 1111 AUC <70 mg/dL
- 1112 Low blood glucose index
- 1113 Frequency of CGM-measured hypoglycemic events (see below):

1114 *Glucose Control*

- 1115 Mean glucose
- 1116 Percentage of values 70 to 180 mg/dL

1117 *Hyperglycemia*

- 1118 Percentage of values >250 mg/dL
- 1119 Percentage of values >180 mg/dL
- 1120 AUC glucose >180 mg/dL
- 1121 High blood glucose index

1122 Each of the metrics listed will be calculated over 24 hours and separately for daytime (6am – 10pm)

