1163 structure will be fit for percent time below <70 mg/dL to compare the two treatments. The
1164 model will adjust for period as a covariate. If residual values from the regression model have a skewed
1165 distribution then an appropriate transformation or a nonparametric analysis based on ranks will be
1166 performed.
1167

1168 There will be no imputation of missing CGM data.
1169

1170 **10.7. Analysis of the Secondary Endpoints**
1171 Analysis of the secondary endpoints and additional CGM metrics will parallel the analysis of the
1172 primary endpoint above.
1173

1174 **10.8. Safety Analyses**
1175 The following safety outcomes will be tabulated by participant within each 3-week treatment period.
1176 The summary statistics will include start date, stop date, severity, relationship, resolution, and duration.

- Diabetic ketoacidosis (DKA), as defined by the Diabetes Control and Complications Trial (DCCT).
- Severe clinical hypoglycemic events such that the participant required assistance from another person to actively administer carbohydrate, glucagon, or engage in other resuscitative actions; note severe hypoglycemia could be considered both and efficacy and safety outcome
- Ketosis events (blood ketone level >1.0 mmol/L)
- All other reported adverse events
- Unanticipated adverse device effects

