129 Total percentage of time PLGS and CGM is used per week will be calculated by dividing the total number of hours of PLGS readings by the maximum possible number of hours within the study period visit dates described above. Number of days of PLGS and CGM use per week is calculated as the count

132 of days during the week where there was at least one PLGS/CGM reading. Data from both study periods
133 will be included in this analysis. No missing data will be imputed.

134

135 **Hypoglycemic Events**

136 A CGM-measured hypoglycemic event will be defined as:

- 137 • at least 2 sensor values < 54 mg/dl
- 138 • that are 15 or more minutes apart
- 139 • no intervening values > 54 mg/dl
- 140 • Event ends when:
 - 141 ➤ at least 2 sensor values > 70 mg/dl
 - 142 ➤ that are 30 or more minutes apart
 - 143 ➤ no intervening values < 70 mg/dl
- 144 • Participant becomes eligible for a new event as soon as the above criteria for ending the previous
145 event have been met.

146

147 **5. Description of Statistical Methods**

148

149 **5.1 General Approach**

150 All analyses will compare the 3-week period of PLGS to the 3-week period of SAP and will follow the
151 intention-to-treat principle with each period analyzed according to the treatment assigned by
152 randomization regardless of actual PLGS or SAP utilization. All participants who have at least one
153 CGM reading in each 3-week period will be analyzed for the primary and secondary outcomes. All p-
154 values will be two-sided.

155

156 Standard residual diagnostics will be performed for all analyses. If values are highly skewed, then a
157 transformation or nonparametric methods will be used instead. Previous experience suggests that a
158 transformation may be necessary for the hypoglycemic and hyperglycemic outcomes. We do not expect
159 that a transformation will be necessary for some overall glucose control metrics (such as mean glucose).

160

161 **5.2 Analysis Cohorts**

- 162 • All randomized participants who have at least one CGM reading in both 3-week periods will be
163 analyzed for the Intention-to-Treat (ITT) Analysis with each day included in the treatment group
164 assigned by randomization.
- 165 • Safety outcomes will be reported for all enrolled participants, irrespective of whether the study was
166 completed.
- 167 • A per-protocol analysis will be restricted to participants with ≥ 200 hours of CGM data in each 3-

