168 week period. This analysis will only involve the primary outcome, and will only be done if at least
169 10% of subjects are excluded based on this criterion.

170

171 **6. Analysis of the Primary Efficacy Endpoint**

172

173 **6.1 Included Subjects**

174 As noted in section 5.2, the primary analysis for this study will include all randomized subjects with at
175 least one CGM sensor reading in each of the two treatment periods. No additional minimum amount of
176 CGM use is required otherwise.

177

178 **6.2 Missing Data**

179 There will be no imputation of missing CGM data for the primary analysis in this study.

180

181 **6.3 Statistical Methods**

182 Mean \pm SD (standard deviation) or summary statistics appropriate to the distribution will be reported for
183 % time below 70 mg/dL for each treatment arm. A repeated measures regression model with an
184 unstructured covariance structure will be fit for percent time below 70 mg/dL to compare the two
185 treatments. The model will adjust for period as a covariate.

186

187 Residual values from the above model will be examined for an approximately normal distribution. It is
188 likely that the residuals themselves will have a skewed distribution, but that the paired differences from
189 the same subject may follow an approximate bell-shaped curve. However, if the paired differences have
190 a skewed distribution, then an appropriate transformation or a nonparametric analysis based on ranks
191 will be performed. Significance will be assessed at the 5% level.

192

193 A carryover effect is not expected, but it will be assessed with a separate model built with the inclusion
194 of a period by treatment interaction. However, the study is not expected to have sufficient power in
195 making definitive conclusions about the period by treatment interaction.

196

197 **7. Analysis of the Secondary Endpoints**

198 The same subjects will be included as in the primary analysis. Missing data will not be imputed for any
199 of the secondary analyses in this study.

200

201 **7.1 Statistical Methods**

202 For all secondary outcomes, summary statistics appropriate to the distribution will be tabulated by
203 treatment group. Analysis of all secondary endpoints will parallel the primary analysis. A ranked normal
204 score transformation will be applied to all highly skewed secondary outcomes.

205

206 **7.2 Secondary Analyses by Time of Day**

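### Does it matter that the protocol and the SAP name different skewness triggers for leaving the untransformed primary model?

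*SAP*

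**What the plan says.** The primary model is the same in both documents: repeated measures regression with unstructured covariance, adjusted for period. They differ on when to leave it.

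- **Protocol 10.6** makes the switch conditional on the model residuals: "If residual values from the regression model have a skewed" distribution, the analysis moves to a suitable transformation or a rank-based method.
- **SAP 6.3** also examines the residuals, but finds it "likely that the residuals themselves will have a skewed distribution, but that the paired differences from" "the same subject may follow an approximate bell-shaped curve. However, if the paired differences have" a skewed distribution, the same two options apply. Skewed residuals alone do not trigger the switch.
- **SAP 5.1**, on the general approach to all analyses, calls for residual diagnostics and adds: "If values are highly skewed, then a" transformation or nonparametric method is used. It expects that a "transformation may be necessary for the hypoglycemic and hyperglycemic outcomes".
- **SAP 7.1** names a method, but for secondary endpoints: a ranked normal "score transformation will be applied to all highly skewed secondary outcomes".
- **Protocol 10.1** says that a detailed "analysis plan will be written and finalized prior to the completion of the study", and that the "synopsis in this chapter contains the framework of the anticipated final analysis plan".

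**The concern.** The SAP predicts the very case in which the two rules part: skewed residuals with roughly bell-shaped paired differences. Read literally, Protocol 10.6 then drops the untransformed model and SAP 6.3 keeps it. SAP 5.1 adds a third wording. Nothing says how much skewness is too much, and the primary fallback is a choice between two classes of method. The secondary endpoints are better specified in this respect than the primary one.

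The primary comparison is the only confirmatory test, and Protocol 1.1 says that the data are meant to support a premarket application. If the choice stayed open until results were known, an analyst could in principle report whichever analysis was significant, and the nominal 5% level would not hold.

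**Working it through.** **1. The plan's own figures.** Inputs: control rate 4% (SAP 11); 33% relative reduction, SD of paired differences 3%, two-sided 5% and 90% power (Protocol 10.3). Taking the reduction as one third, the difference is 4/3 = 1.333 points.

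N = [3 × (1.960 + 1.282) / 1.333]² = 53.2, so 54, against the stated 52.

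Power at N = 90: 1.333/3 × √90 = 4.216; Φ(4.216 − 1.960) = 98.8%, against the stated 99%.

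The agreement is close. The calculation is for untransformed paired differences, so it matches the analysis that SAP 6.3 starts from.

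**2. Which diagnostic matters.** Everyone analysed has data in both periods. The period-adjusted treatment estimate is then the average of the two sequence means of the PLGS-minus-SAP difference, and its standard error comes from the spread of those differences. A participant's general level of hypoglycemia, the main source of skewed residuals, cancels. With no treatment or period effect the two values are exchangeable and their difference is symmetric, however skewed each value is. The expectation in SAP 6.3 is therefore well founded.

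**3. What the difference between the rules does.** The documents give no distribution or cut-off, so these are assumptions: 90 participants (45 per sequence); participant level gamma with shape 1.3 and mean 4; independent gamma period multipliers with mean 1 and shape k; treatment multiplying the value by (1 − effect). Rule: absolute skewness above c selects ranked normal scores, otherwise raw values. 20,000 trials per cell.

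| | k = 4 | k = 5.2 | k = 6 |
|---|---|---|---|
| SD of differences at 33% | 3.40 | 3.04 | 2.86 |
| Different analysis chosen at 33%, c = 1 | 25.6% | 22.1% | 20.1% |
| Different verdict at 33%, c = 0.5 | 0.65% | 0.15% | 0.04% |
| Different verdict at 33%, c = 1 | 1.11% | 0.29% | 0.10% |
| Different verdict at 33%, c = 1.5 | 1.40% | 0.39% | 0.15% |

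With no effect, the rules choose different analyses in 29 to 67% of trials, yet each holds its level. For k = 5.2 and c = 1, type I error is 4.10% under the paired-difference rule and 4.98% under the residual rule. Over all settings the ranges are 4.1 to 4.4% and 5.0 to 5.2%. Choosing raw or rank by p-value gives 7.2 to 7.6%.

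At the planned 33% reduction, power is 98.5 to 99.96% under the paired-difference rule and 99.8 to 100% under the residual rule. Median skewness of the differences is then about −1.6 to −1.7, so both rules usually leave the untransformed model.

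**The case for a change.** The strongest reply is that the reassurance depends on the planned effect. At a 15% reduction in the same model, the two rules give different verdicts in 6 to 15% of trials. With c = 1, power is about 44 to 58% under the paired-difference rule and 53 to 70% under the residual rule. A separate log-normal simulation agrees: at 15%, four admissible analyses (raw, log, normal scores, signed rank) disagree on significance in about 35% of trials, and taking the best of the four gives about 9% type I error. No sentence says that SAP 6.3 prevails, SAP 5.1 leans back towards residuals, and the SAP cites protocol version 5.0 while the protocol supplied is 6.0. Even SAP 6.3 alone leaves the cut-off and fallback open.

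The textual points stand, and a sentence on precedence would have been tidier. They do not make the plan wrong:

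- The 7% and 9% figures are upper bounds for choosing by p-value. Both documents make the switch depend on shape.
- The results at 15% show a trade-off. Enforcing the SAP trigger would settle on the less powerful rule at small effects; enforcing the protocol trigger would act on skewness that largely cancels from the test.
- A numerical cut-off, such as absolute skewness of 1, has no basis in the documents.
- Applying the cut-off to differences centred within sequence would not hide the treatment effect. In this model median centred skewness is about 0 with no effect and about −1.6 at 33%, where it is negative in 92 to 95% of trials.

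**Conclusion.** No change follows. The wordings differ, and the criterion and primary fallback are left to judgment. But Protocol 10.1 delegates detail to the SAP, SAP 6.3 is the section specific to the primary endpoint, and its diagnostic fits the test. SAP 5.1 is general guidance, and its remark about hypoglycemic outcomes is an expectation. SAP 7.1 offers an obvious fallback.

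Either rule, followed as written, holds type I error at about 4 to 5%. At the planned effect the verdict changes in at most 1.4% of trials, and in 0.15 to 0.39% when the SD of differences is near the planned 3. These sizes rest on the assumed gamma model, cut-offs of 0.5 to 1.5, ranked normal scores as fallback, and 90 participants with both periods. At effects well below plan the choice affects power and sometimes the verdict, but that reflects two valid analyses with different sensitivity and does not make either invalid.

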58 may be randomized into the crossover trial. Immediately after randomization, subjects will enter the two
59 3-week study periods (21 days each) and will test one intervention per study period, using either the
60 PLGS or SAP system first. The interventions will not be separated by a washout period.
61

62 **2. Statistical Hypotheses**

- 63 • *Null Hypothesis*: There is no difference in the mean time spent below 70 mg/dL over the 21-day
64 period between the two treatment groups.
- 65 • *Alternative Hypothesis*: There is a nonzero difference in the mean time spent below 70 mg/dL
66 over the 21-day period between the two treatment groups.
67

68 **3. Sample Size**

69 The study is projected to include at least 90 subjects. Of these study participants, at least 45 will be $<$ 18
70 years old, and at least 45 will be \geq 18 years old. Of the 45 participants that are $<$ 18 years old, at least 15
71 participants will be 12 to 17 years old, and at least 15 will be 6 to 11 years old. The 90 study participants
72 will also include a minimum of 15 pump users, 15 multiple daily injection of insulin (MDI) users, 15
73 CGM naïve users (may be pump or MDI users), and 15 experienced CGM users (may also be pump or
74 MDI users).
75

76 The subjects will be randomized to the order of the interventions based on a 1:1 ratio. Randomization
77 will not be stratified.
78

79 **4. Outcome Measures**

80 **4.1 Primary Efficacy Endpoint:**

81 Percent of CGM glucose sensor values < 70 mg/dL

83 **4.2 Secondary Efficacy Endpoints:**

84 *CGM Metrics*

85 Overall Glucose Control

86 1) Mean of CGM glucose sensor values

87 2) Percent of CGM glucose sensor values between 70 and 180 mg/dL (not inclusive of the
88 limits)

89 Hypoglycemia

90 3) Percent of CGM glucose sensor values < 60 mg/dL

91 4) Percent of CGM glucose sensor values < 50 mg/dL

92 5) Area over curve for CGM glucose sensor values < 70 mg/dL.

93 6) Low blood glucose index (LBGI).

94 7) Frequency of CGM-measured hypoglycemic events per week (see below)

95 Hyperglycemia

96 8) Percent of CGM glucose sensor values > 250 mg/dL

97 9) Percent of CGM glucose sensor values > 180 mg/dL

98 10) Area under curve for CGM glucose sensor values > 180 mg/dL.

99 11) High blood glucose index (HBGI)

101 **4.3 Calculation of CGM Metrics**

102 Each metric will be calculated for CGM sensor values over the entire 24-hour period.

103

104 Primary Outcome - % Time Below 70 mg/dL

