207 Each of the secondary outcomes will be calculated separately for sensor values during daytime (6:00
208 AM to just before 10:00 PM) and sensor values during nighttime (10:00 PM to just before 6:00 AM).

209 The primary outcome, percentage of glucose sensor values < 70 mg/dL, will also be divided into
210 daytime and nighttime periods as an additional secondary outcome.
211
212 For all secondary outcomes separated by time of day, summary statistics appropriate to the distribution
213 will be tabulated by treatment group. The same model described above for the primary and secondary
214 analyses will be fit with the inclusion of a treatment by time of day interaction. The p-value for the
215 interaction term will be reported. These analyses will be conducted to determine whether a similar trend
216 to the overall treatment effect is seen in the different times of day. An appropriate transformation or a
217 nonparametric analysis based on ranks will be applied to all highly skewed secondary outcomes.
218
219 The study is not expected to have sufficient statistical power for definitive conclusions in the secondary
220 analyses by time of day, and statistical power will be low to formally assess a treatment by time-of-day
221 interaction. Interpretation of the analyses by time of day will depend on whether the overall analysis
222 demonstrates a significant treatment effect. In the absence of any significant treatment effects in the
223 overall analyses, assessment of secondary analyses by time of day will be considered exploratory and
224 used to suggest hypotheses for further investigation in future studies.
225

226 **8. Safety Analyses**

227

228 Safety outcomes will be tabulated by participant for all adverse events from enrollment to the final study
229 visit or final adverse event, whichever comes later.
230

231 **8.1 Definitions**

232 Reportable adverse events for this protocol include severe hypoglycemia (SH), diabetic ketoacidosis
233 (DKA), and any other untoward medical occurrence that meets criteria for an adverse event (AE) or
234 serious adverse event (SAE). Device deficiencies that could have led to an adverse device effect will
235 also be reported.
236

237 Hypoglycemic events will be considered severe if the participant required assistance from another
238 person to actively administer carbohydrate, glucagon, or engage in other resuscitative actions. This

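### The day and night hypoglycemic-event frequencies are calculated on readings split at 06:00 and 22:00, which miscounts events that cross a limit; a single-assignment rule is needed.

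*SAP*

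**What the plan says.** SAP 7.2 sets the rule for the time-of-day analyses: "Each of the secondary outcomes will be calculated separately for sensor values during daytime" (06:00 to just before 22:00) and, separately, for the nighttime values (22:00 to just before 06:00). Protocol 10.4 applies the same split: "Each of the metrics listed will be calculated over 24 hours and separately for daytime" and nighttime.

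One of the outcomes covered is SAP 4.2, item 7: "Frequency of CGM-measured hypoglycemic events per week (see below"). SAP 4.3 defines the event:

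- **Start:** "at least 2 sensor values < 54 mg/dl", "that are 15 or more minutes apart", with nothing above 54 mg/dL between them.
- **End:** two values above 70 mg/dL, "that are 30 or more minutes apart", with nothing below 70 mg/dL between them.
- **Eligibility:** the participant can begin another event only once the previous one has met the end rule.

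SAP 4.3 also says that secondary metrics are computed in the same way as the primary outcome, which pools readings. Neither document says how to treat an event that spans 06:00 or 22:00.

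SAP 7.2 reports a treatment by time-of-day interaction p-value for these outcomes, and SAP 13 gives them their own false-discovery-rate family. SAP 7.2 also says that power is low and that interpretation depends on the overall result.

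**The concern.** Filtering readings by clock time and then computing the metric is sound when each reading contributes on its own. An event is a sequence. Cutting the sequence at a clock limit can leave too little on either side to meet the 15-minute start rule, so the event is lost. It can also leave enough on both sides to meet the rule twice. The recovery that ends a night event may also fall in the day readings.

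The miscount depends on event length, and Protocol 1.1 describes a device meant to reduce both how often hypoglycemia occurs and how long it lasts. If event length differs between arms, a length-dependent miscount can appear as a difference in event frequency. The night window is half as long as the day window, so the proportional error there is twice as large, and this feeds into the interaction that SAP 7.2 tests. Day and night counts also need not add up to the 24-hour count.

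**Working it through.** The plan states no figure for this point, so there is none to reproduce.

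**Inputs from the documents.** One reading every 5 minutes (Protocol 1.2), so 288 per day: 96 in the 8-hour night and 192 in the 16-hour day. A 15-minute span needs 4 consecutive low readings.

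**Assumptions, not in the documents.** Onsets are uniform over 24 hours. Each event is a single run of n consecutive readings below 54 mg/dL, with span 5(n−1) minutes. Event lengths are illustrative.

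**What happens at one limit.** A crossing run leaves k readings before the limit and n−k after it, with k from 1 to n−1.

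- It vanishes if both parts have 3 readings or fewer: 7−n positions for n = 4, 5, 6 (3, 2 and 1), and none from n = 7.
- Both parts meet the start rule if each has 4 readings or more: n−7 positions for n ≥ 8.

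Over the two daily limits, vanishing positions are 6 of 6 at 15 min, 4 of 8 at 20 min and 2 of 10 at 25 min. Positions that can double are 4 of 16 at 40 min, 12 of 24 at 60 min and 24 of 36 at 90 min.

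**Reading A: eligibility restarts at the limit.** A run registers in a window if at least 4 of its readings fall there. For the night this gives 96 + (n−1) − 6 = 96 + n − 7 onset positions, against 96 when events are assigned by onset. So

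- night ratio = 1 + (n−7)/96
- day ratio = 1 + (n−7)/192
- day plus night per true event = 1 + (n−7)/144

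**Reading B: SAP 4.3 eligibility carries across the limit.** For n ≥ 7, a run with 4 or more readings before the limit counts in the earlier window and is then blocked. A run with 1 to 3 readings before it counts only in the later window. At 06:00 the night loses 3 positions to the day, and at 22:00 it gains 3, so the ratio is 1.000 in both windows. For n = 4 to 6 no run can double, so the results equal reading A.

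| Span (min) | n | Night, A | Day, A | Night, B | Day, B |
|---|---|---|---|---|---|
| 15 | 4 | 0.969 | 0.984 | 0.969 | 0.984 |
| 20 | 5 | 0.979 | 0.990 | 0.979 | 0.990 |
| 25 | 6 | 0.990 | 0.995 | 0.990 | 0.995 |
| 30 | 7 | 1.000 | 1.000 | 1.000 | 1.000 |
| 60 | 13 | 1.063 | 1.031 | 1.000 | 1.000 |
| 90 | 19 | 1.125 | 1.063 | 1.000 | 1.000 |

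Enumerating all 288 onset positions agrees with the closed forms.

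**Effect on the arm comparison under reading A**, with equal true event rates and PLGS events assumed to last 30 min:

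- SAP-therapy events of 60 min: night 1/1.0625 = 0.941; day 1/1.03125 = 0.970; night-to-day ratio 0.971.
- SAP-therapy events of 90 min: night 1/1.125 = 0.889; day 1/1.0625 = 0.941; night-to-day ratio 0.944.

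With equal lengths in both arms, every one of these ratios is 1.

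**Limits of the calculation.** Under reading A, onsets clustered near a limit, or repeated dips without 30 minutes of recovery, would raise the double counting. Separately, if night readings were joined across days, low values at 05:55 and at 22:00 would satisfy the 15-minute wording and create a false event.

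**The case against.** The strongest reply is the eligibility rule in SAP 4.3, repeated in Protocol 10.4. Eligibility belongs to the participant, not to a clock window. Someone low from 05:30 to 06:30 has not recovered at 06:00, so no new event can begin there. This stands as a fair reading, and it removes all the double counting. It does not remove the loss of crossing events of 25 minutes or less, because the start rule is still applied to cut data.

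A second reply is that a programmer could find events on the full trace and classify them afterwards, which would leave no error. That is possible, but SAP 7.2 describes selecting sensor values by clock time and gives no instruction to treat this outcome differently.

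A third reply is that the consequence is limited. This is one metric of eleven, in an analysis that the SAP itself calls underpowered. That is correct, although low power does not remove a systematic miscount. On the ratio scale, the distortion of the interaction is also about half that of the night comparison.

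A reader might infer that the plan will show a spurious 6% to 11% night benefit for PLGS. The documents do not support that. It requires eligibility to restart at the limit, which neither document says, and event lengths by arm, which neither document gives. The design aim in Protocol 1.1 concerns incidence as well as duration. If PLGS mainly prevented brief events, the remaining events would be longer on average and the bias under reading A would run against PLGS.

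**Conclusion.** The point holds as a limited but real defect. Splitting readings at 06:00 and 22:00 does not suit an episode endpoint, and some miscount remains whether or not eligibility carries across the limit.

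- **Certain under either split reading:** some or all crossing events of 25 minutes or less are lost, with the night count up to 3% low and the day count up to 1.6% low.
- **Only if eligibility restarts:** events of 35 minutes or more with at least 15 minutes on each side count twice (night +6% and day +3% at 60 min; night +12.5% and day +6% at 90 min).
- **Between arms:** conditional on unequal event lengths as well. At an assumed 30 against 60 to 90 minutes, the night rate ratio is 0.94 to 0.89 and the night-to-day ratio 0.97 to 0.94 with no true difference.

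All figures assume uniform onsets and a single dip per event. The primary endpoint, the 24-hour event rate, and the percentage, mean and index metrics are unaffected.

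**What to change.** Add a sentence to SAP 7.2 for outcome 7: events are identified once on the continuous 24-hour trace by the SAP 4.3 start, end and eligibility rules, and each event is assigned once to day or night by a fixed rule, for example the clock time of its first value below 54 mg/dL. Onset time is one workable convention. What matters is that the rule is fixed and assigns each event once. Day and night counts then sum to the 24-hour count at every event length, and no false event can arise from joining separate nights. The events-per-week denominator can stay; changing it to CGM hours is not needed for this fix.

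The cost is one sentence and a small programming change, with no new data. The night contrast may come out slightly smaller than under a split with eligibility restarting.
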